**Table 1 Possible Sample Sizes**

Emicizumab Adoption	5%	15%	25%	50%	75%
Number of patients with severe disease treated with emicizumab a	-	-	293	587	880
Number of patients with inhibitor treated with emicizumab a	-	-	88	176	263
Number of patients with moderate disease treated with emicizumab a	11	34	56	-	-

a based on N=1173 patients with severe disease, N=351 with severe disease and with inhibitor, and N=225 with moderate disease enrolled in the PedNet Registry as of January 2019

## 8.6 DATA MANAGEMENT

As per the PedNet Registry protocol, data is collected and updated on each regular visit to the center. The data entry environment is web based and secured by personal login and password. Forms are completed and submitted to the central database in the Julius Center of Health Sciences and Primary Care of the University Medical Center Utrecht, The Netherlands. The data system meets GCP guidelines (ISO 9001:2000 since 2005) and is FDA compliant (21 CFR part 11). No personal data is provided to Roche/Genentech.

## 8.7 DATA ANALYSIS

### Data transformation

The MAH will receive aggregate level data of patients treated with emicizumab from the PedNet Registry on an annual basis.

Based on the number of patients, number of AEs, and exposure to emicizumab provided by the Registry, the MAH will perform analyses of frequencies/incidence of AEs overall and grouped by age and status of inhibitor as well as by severity for patients without inhibitors. The youngest age group will be newborn (birth to 28days). Other age groups include: 29 days-<6 months, 6 months-<2 years, 2 years-<6 years, 6 years-<12 years, 12 years-18 years. The MAH will report ABR for treated bleeds, percentages of zero bleeds, ABR for joint bleeds and major bleeds overall and grouped by age and status of inhibitor as well as by severity for patients without inhibitors as sent by PedNet registry. ABRs for soft tissue bleeds and minor bleeds is not calculated by PedNet and therefore only the number of bleeds will be presented.

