While the results observed in the clinical trials supporting the benefit-risk assessment at the time of the marketing authorization application are compelling and demonstrate a favorable benefit-risk profile, experience with emicizumab in the pediatric population has been primarily based on pediatric patients with inhibitors. In addition, there is no clinical experience with emicizumab use in newborns (birth to Day 28 of life), who are vulnerable to development of severe bleeds. The post-approval evaluation of the drug's outcomes and utilization is vital to assessing whether the efficacy and safety profile observed in clinical trials match the real-world experience in all age groups. To address this, data collected by the Pediatric Network on haemophilia management (PedNet) Registry is extracted and analyzed according to the current protocol, and Annual Reports is generated.

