### **8.3.2 Secondary Variables**

The secondary variables for this study are as follows:

- Other AEs reported to the Registry including new inhibitor development, unexpected poor efficacy (unexpected poor efficacy is included in “Other” category of AE collection in the PedNet Registry eCRF).
- Bleeding event (yes/no)
- Bleed location (joint bleed, soft tissue bleed), severity (major vs. minor\*)

\*Note PedNet protocol bleed definitions are as follows:

- Major bleed: Bleed characterized by pain, swelling, limitation of motion and failure to respond within 24 hours of treatment
- Minor bleed: Bleed characterized by minor pain, minimal swelling, minimal restriction of motion, and resolving within 24 hours of treatment
- Joint bleed: any complaint requiring treatment located in a joint
- Soft tissue bleed: any complaint requiring treatment located outside the joints
- Concomitant administration of coagulation factor concentrate products (type and dose of product FVIII product, aPCC, rFVIIa) in patients receiving emicizumab.

The baseline variables for this study are as follows (baseline is defined as the time of starting emicizumab):

- Diagnosis of hemophilia A
- Exposure to emicizumab (prophylaxis)
- Age
- FVIII Inhibitor status

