### 8.7.1 Primary Analyses

The primary AEs are TE, TMA, and anaphylaxis. Additional AEs including inhibitor development and unexpected poor efficacy will be included as they are collected by PedNet Registry.

Adverse events collected in PedNet are not collected according to MedDRA classification. Most events are collected according to pre-specified lists; however, free-text fields are also available for each event. Whenever possible, AEs will be reclassified by Roche according to MedDRA PT level using the most current MedDRA version.

Primary analyses: For each AE of interest (TMA, TE, and anaphylaxis), the following analysis will be performed overall and grouped by age and status of inhibitor as well as by severity for patients without inhibitors:

- Annual incidence rate of the AE among patients exposed to emicizumab will be estimated as the number of patients who were treated with emicizumab and developed the AE, divided by the person years of emicizumab exposure. The numerator will be calculated using report from PedNet.
- PedNet will provide number of patients treated with emicizumab and emicizumab mean exposure days, which will be used to calculate the person years of emicizumab exposure using the following formula:

Person years of emicizumab exposure=[number of patients exposed to emicizumab×mean emicizumab exposure time in days–number of patient exposed to emicizumab and had event×(mean emicizumab exposure time in days/2\*)]/365.25

\*Note that this calculation accounts for patients who are censored in the study once they have experienced an adverse event (event is imputed to happen after half the exposure time).

Exact binomial 95% confidence intervals will be calculated for each incidence rate.

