### **8.7.2            Secondary analyses:**

- Annual incidence proportion of AE of interest (TMA, TE, and anaphylaxis) among patients exposed to emicizumab will be estimated as the number of patients who were treated with emicizumab and developed the AE, divided by the number of patients who are exposed to emicizumab. The incidence proportion will be calculated overall and by age and status of inhibitor as well as by severity for patients without inhibitors.
- For each AE of interest (TMA, TE, and anaphylaxis), the following proportions will be calculated, together with the corresponding 95% confidence intervals:
  - Annual incidence proportions of the AE among patients treated with emicizumab and concurrently with each of the following drugs: aPCC, rFVIIa, and FVIII product.
- Annual number and percentage of each of the other adverse events reported to PedNet will be presented. Currently, in addition to TE, TMA, and anaphylaxis, these events may include: new inhibitors, allergic reactions, local subcutaneous reaction, other AEs including unexpected poor efficacy.
- ABRs: Estimates for the ABR are based on a negative-binomial model adjusted for age group and inhibitor status. The negative-binomial models each use the “total number of bleeds” (for each specified type of bleed) as the outcome and the model is offset by the “total duration of follow-up” since first exposure to emicizumab.

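### Section 8.7 sets age bands as narrow as birth to 28 days without saying when age is taken; read with the rest of the protocol, the newborn incidence rate is built almost wholly on exposure after the newborn period.

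*Protocol*

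**What the plan says.** Section 8.7 (Data transformation) has the sponsor analyse adverse event incidence overall and by age, inhibitor status and, for patients without inhibitors, severity. It fixes the bands: "The youngest age group will be newborn (birth to 28days", and then "Other age groups include: 29 days-<6 months, 6 months-<2 years, 2 years-<6 years, 6 years-<12 years, 12 years-18 years". It does not say at what moment a patient's age is read.

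Age appears as a defined variable in one place, the list of baseline variables in Section 8.3.2, where "baseline is defined as the time of starting emicizumab".

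For the primary safety rates, Section 8.7.1 says "PedNet will provide number of patients treated with emicizumab and emicizumab mean exposure days". Person-years start from "number of patients exposed to emicizumab×mean emicizumab exposure time in days", less half the mean exposure for each patient with an event, because the "event is imputed to happen after half the exposure time". No step divides exposure by age reached.

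For bleeding, the negative-binomial model in Section 8.7.2 takes each patient's total bleed count, adjusts for age group and inhibitor status, and uses as offset the total follow-up "since first exposure to emicizumab".

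Newborns are a stated target. The synopsis rationale says that "there is no clinical experience with emicizumab use in newborns". The synopsis data analysis section promises results for newborns, and its milestones section times the first extraction to obtain early data in newborns and infants.

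**The concern.** A 28-day band and follow-up measured in years do not fit together unless patients move between bands as they grow. If the band is fixed at the first dose, a child started on day 10 stays in the newborn group for every later exposure day. An event or bleed at age 3 would then be counted against newborn person-years.

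Two things are at stake. First, the rate labelled newborn would mostly reflect risk at older ages, in the very group for which the protocol says evidence is lacking. Second, the large denominator would give a narrow interval, so that few or no events could be read as reassurance about a period in which almost no exposure was observed. These age-grouped rates belong to the primary analysis and feed the annual reports to PRAC. Under Sections 8.8 and 9.1 the sponsor receives only aggregates, so it cannot re-split the time itself later.

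**Working it through.** **The plan's own figures.** The protocol gives no person-time, follow-up or rate by age group, so there is none to reproduce. Its anticipated sample sizes (Section 8.5, Table 1) are registry count × adoption and do reproduce (1173 × 0.50 = 586.5, stated as 587; 351 × 0.50 = 175.5, stated as 176; 225 × 0.15 = 33.75, stated as 34). They are not split by age.

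**Inputs**
- Band widths (Section 8.7): newborn 28 days; 29 days to <6 months, 182.6 − 29 = 153.6 days; 6 months to <2 years, 730.5 − 182.6 = 547.9 days.
- Study span: first extraction November 2019, last January 2025 (Section 5); Section 8.5 speaks of 6 years.
- Follow-up per patient, F: not given. Assumed range 1 to 6 years.

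**Share of a starter's follow-up that lies inside the starting band.** Maximum share = min(band width, F) / F.

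| Starting band | F = 1 year | 2 years | 5 years | 6 years |
|---|---|---|---|---|
| Newborn | 28/365.25 = 7.7% | 28/730.5 = 3.8% | 28/1826.25 = 1.5% | 28/2191.5 = 1.3% |
| 29 days to <6 months | 42% | 21% | 8% | 7% |
| 6 months to <2 years | 100% | 75% | 30% | 25% |

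These maxima apply to a child who starts at the lower edge of the band. If start ages are spread evenly over the band (an assumption), the average newborn shares are about half: 3.8% at 1 year and 1.9% at 2 years. For 6 months to <2 years the averages are 67% at 1 year, 37.5% at 2 and 15% at 5.

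**Effect on the denominator (illustration).** Assume 10 newborn starters with a mean exposure of 2 years.
- Formula in Section 8.7.1, no events: 10 × 730.5 / 365.25 = 20.0 person-years. With one event: (7305 − 365.25) / 365.25 = 19.0.
- Time actually in the newborn period: at most 10 × 28 / 365.25 = 0.77 person-years, or 3.8% of 20.0.

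**Effect on apparent precision.** With zero events, the upper limit of a two-sided 95% exact Poisson interval (used here only for illustration) is 3.69 divided by person-years.
- As the plan reads: 3.69 / 20.0 = about 18 per 100 person-years.
- On newborn time only: 3.69 / 0.77 = about 481 per 100 person-years.
- Ratio: 20.0 / 0.77 = about 26.

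**Internal check.** The formula places an event at half the mean exposure. Once mean exposure exceeds 56 days, that point is more than 28 days after the first dose. At 2 years it is about day 365 of exposure, so the formula's own assumption puts a newborn event well outside the newborn period.

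**The case against.** The strongest objection is that Section 8.7 never says age is taken at the first dose. The baseline list in Section 8.3.2 is descriptive and is not tied to the subgroup rule, and the age basis is a detail that could sit in a statistical analysis plan. The person-years formula would also run unchanged if the registry supplied patient numbers and mean days per attained-age band. This stands to a degree: a reader might infer that the protocol expressly assigns patients by age at first dose, and it does not. What remains is that the bands, the formula and the aggregate data request are all fixed here, the only defined age is baseline age, and nothing directs a split. The text is firmer for the ABR model, where total bleeds over total follow-up leave one age group per patient.

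Other limits also stand. A reader might conclude that all infant rates are almost wholly older time. That is too strong for 6 months to <2 years, where up to 75% of time can stay in band at 2 years, and no band is labelled infant. A reader might also conclude that the events, and not only the time, lie at older ages. The documents give no event timing, so this cannot be said. Section 8.1 asks for detailed data on patients with TE, TMA or anaphylaxis, which may show the age at each event; that helps the numerator but leaves the denominator as it is.

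Finally, grouping by age at start is legitimate. It answers what happens to children who begin emicizumab as newborns. That is a different question from the risk during the newborn period, and the tables need to show which one is being answered.

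**Conclusion.** The point holds in limited form. The protocol leaves the age basis in Section 8.7 unstated, and the natural reading of its sections together credits years of later exposure to the starting band. For newborns, at least 92% of the person-time (1 year of follow-up) and up to about 99% (6 years) would lie outside the newborn period. For 29 days to <6 months, at least 58% would lie outside at 1 year and at least 79% at 2 years. From 6 months upward the effect is smaller and depends strongly on follow-up.

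The conclusion rests on two assumptions: that age at start is the intended basis, which is an inference from Section 8.3.2, and that follow-up is 1 to 6 years. The misallocated person-time follows from these alone. The number of misplaced events, and hence the size of any bias in the rate, cannot be derived from the documents. The change should be made because newborns are a named evidence gap and the sponsor cannot rebuild the split from aggregates.

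**What to change.** 1. State in Section 8.7 when age is taken for each age-grouped result.
2. For the incidence rates in Section 8.7.1, ask the registry for the number of patients contributing time, the exposure days, and the first TE, TMA and anaphylaxis events in each attained age band, and calculate the age-specific rates from these. If the registry stops each patient's exposure at the actual event date, the half-exposure deduction is no longer needed for these rates.
3. Label incidence proportions, percentages with zero bleeds and ABR groups as age at emicizumab start. If ABR is also split by attained age, each patient contributes several records, and the negative-binomial model must account for that correlation.

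The cost is a small extra tabulation at the registry, which already does the extraction and analysis; no patient-level data need reach the sponsor. The drawback is that the newborn band will show very little person-time and wide intervals, which is the information actually available.

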### 8.7.1 Primary Analyses

The primary AEs are TE, TMA, and anaphylaxis. Additional AEs including inhibitor development and unexpected poor efficacy will be included as they are collected by PedNet Registry.

Adverse events collected in PedNet are not collected according to MedDRA classification. Most events are collected according to pre-specified lists; however, free-text fields are also available for each event. Whenever possible, AEs will be reclassified by Roche according to MedDRA PT level using the most current MedDRA version.

Primary analyses: For each AE of interest (TMA, TE, and anaphylaxis), the following analysis will be performed overall and grouped by age and status of inhibitor as well as by severity for patients without inhibitors:

- Annual incidence rate of the AE among patients exposed to emicizumab will be estimated as the number of patients who were treated with emicizumab and developed the AE, divided by the person years of emicizumab exposure. The numerator will be calculated using report from PedNet.
- PedNet will provide number of patients treated with emicizumab and emicizumab mean exposure days, which will be used to calculate the person years of emicizumab exposure using the following formula:

Person years of emicizumab exposure=[number of patients exposed to emicizumab×mean emicizumab exposure time in days–number of patient exposed to emicizumab and had event×(mean emicizumab exposure time in days/2\*)]/365.25

\*Note that this calculation accounts for patients who are censored in the study once they have experienced an adverse event (event is imputed to happen after half the exposure time).

Exact binomial 95% confidence intervals will be calculated for each incidence rate.

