## **8. RESEARCH METHODS**

### **8.1 STUDY DESIGN**

This is a non-interventional (NI) secondary data use Post-Authorization Safety Study (PASS) relying on data collected as part of the PedNet Registry. PedNet Registry will extract data (e.g., all variables) indicated in this protocol, perform the statistical analysis and provide results to the Marketing Authorization Holder (MAH) as an aggregated report. Based on this, the MAH will generate an annual PASS report and submit it to the Pharmacovigilance Risk Assessment Committee (PRAC) and/or include the annual report in the periodical benefit risk evaluation report (PBRER) depending on the time of availability of the reports.

PedNet is a multicenter, observational research database that includes patients with FVIII/IX levels < 25 IU/dL born after 1 January 2000 and treated in one of the participating Hemophilia Treatment Centers (HTCs). At the time of protocol amendment, 32 centers from 19 countries are participating in the Registry. The goal of the Registry is to include full cohorts of all consecutive patients diagnosed and treated in each center of which information on treatment and outcomes (e.g., inhibitor development, bleeds) is collected from the time of hemophilia diagnosis or time of first treatment. To prevent selection bias, patients referred to a center after development of inhibitors are not included in the database.

Data included in the Registry is collected using electronic case report forms (eCRFs). Baseline data that pertains to mode of delivery, neonatal events, diagnostic symptoms, FVIII/IX gene mutation, and family history of hemophilia and inhibitors is collected. All centers collect detailed data on treatment and outcomes (including inhibitor development and bleeds) of patients with hemophilia during the first 50 days of exposure to coagulation factor concentrate products. Following this, the centers continue to collect information at least annually until the patient reaches the age of 18. Additional information are collected regarding surgeries, hospitalizations, and AEs.

A similar level of detail is collected for patients treated with emicizumab prophylaxis. When patients treated with emicizumab receive coagulation factor concentrate products, the type of the products is recorded. It is therefore possible to evaluate the relationship between the use of FVIII/BPAs and development of TE/TMA events for patients treated with emicizumab prophylaxis.

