PedNet emicizumab specific report includes patients who are treated with emicizumab. The following data includes in the reports: number of patients treated with emicizumab, duration of emicizumab exposure, number of TE, TMA, anaphylaxis, and any other AEs,

ABR for treated bleeds, percentage of zero bleeds, ABR for joint bleeds, ABR for soft tissue bleeds, ABR for major or minor bleeds, number of patients which have used bypassing aPCC agents when treated with emicizumab, number of patients which have used FVIII products when treated with emicizumab, the number of patients used rFVII when treated with emicizumab and detailed data for patients who have developed TE, TMA or and anaphylaxis. Based on the PedNet annual report, the MAH produces the PASS report annually with the following information grouped by age and status of inhibitor as well as by severity for patients without inhibitors and/or include the results in the annual PBRRER depending on the time of availability of PedNet reports:

- Number of patients exposed to emicizumab (directly from PedNet report)
- Number of patients exposed to emicizumab who experienced TE, TMA, and anaphylaxis (calculated from PedNet report)
- Proportion and incidence of each AE of TE, TMA, and anaphylaxis among patients receiving emicizumab (calculated based on information from PedNet report)
- Number of patients exposed to emicizumab and each of the following drugs: aPCC, rFVIIa, FVIII (directly from PedNet report)
- Number of patients exposed to emicizumab and each of the following drugs: aPCC, rFVIIa, FVIII, who experienced TE, TMA, and anaphylaxis (calculated from PedNet report)
- Proportion of TE and of TMA among patients exposed to emicizumab and each of the following drugs: aPCC, rFVIIa, and FVIII (calculated based on information from PedNet report)
- Number of any other AE and number of patients with any other AE (including inhibitor development, unexpected poor efficacy, local subcutaneous reactions) reported to PedNet Registry (directly from PedNet report)
- ABR for treated bleeds, percentage of zero bleeds, ABR for joint bleeds and ABR for major bleeds (directly from PedNet report)
- Bleeds count for soft tissue bleeds and minor bleeds

PedNet performs annual data extractions in January of each year. Following each data extraction, PedNet group analyzes the data according to this protocol and provide the MAH with Annual Emicizumab-Specific Reports.

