## **8.8                    DATA QUALITY ASSURANCE AND QUALITY CONTROL**

The MAH will maintain adequate and accurate records to enable the conduct of the study to be fully documented, including but not limited to the protocol and protocol amendments. The PedNet registry is responsible for data quality assurance and quality control. All procedures including data collection, storing, monitoring, and quality assurance will be done by PedNet Registry independent of the MAH following European Guidelines and the advice from the European Science Foundation. The Registry has a central coordinator and three regional coordinators with the task of data monitoring.

Every center will be visited before start of inclusion and at the closing of the Registry. Centers will be visited regularly according to their size.

No individual patient data will be transferred to the MAH.

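### Deducting half the mean exposure per event patient does not censor at the event, and the numerator of the primary rate is not explicitly limited to exposed time

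*Protocol*

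**What the plan says.** Protocol section 8.7.1 makes the incidence rate of TE, TMA and anaphylaxis the primary analysis, overall and by age, inhibitor status and, without inhibitors, severity. The rate is the "number of patients who were treated with emicizumab and developed the AE, divided by the person years of emicizumab exposure".

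For the denominator, "PedNet will provide number of patients treated with emicizumab and emicizumab mean exposure days". The sponsor rebuilds person-years from these two figures: patients times mean exposure, minus half the mean exposure for each patient with the event, divided by 365.25. A note explains that patients are meant to be censored once they have an event, and that the "event is imputed to happen after half the exposure time".

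The sponsor sees aggregates only; section 8.8 states "No individual patient data will be transferred to the MAH". The patient-level work is done by the registry, which under section 8.1 is to "perform the statistical analysis and provide results to the Marketing Authorization Holder (MAH) as an aggregated report". That report also covers duration of exposure and "detailed data for patients who have developed TE, TMA or and anaphylaxis". In section 8.7.2 the bleeding-rate model is offset by total follow-up "since first exposure to emicizumab".

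**The concern.** There are two separate weaknesses, one in each half of the primary rate.

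**Denominator.** Censoring at the event means subtracting the exposure that came after it. The formula subtracts half the group mean instead, whatever happened to the patient. If emicizumab exposure ended at the event, there is no later exposure to subtract, and the deduction takes away time that was never in the total. If the event was early and treatment went on, half the mean is usually too little, and time after the event stays in. The sign of the error depends on facts that the number of patients and the mean exposure do not show.

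**Numerator.** The denominator is exposed time. The numerator is any treated patient who developed the event, and no sentence requires the event to fall after the first dose or within a stated period after the last one. Section 8.3.1 restricts by patient, not by time. The registry follows children from diagnosis or first treatment (section 8.1), and the anaphylaxis endpoint includes systemic hypersensitivity (section 8.3.1). A qualifying event outside emicizumab exposure is therefore conceivable. If event counts are near zero, a single such event would change what the rate says.

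**Working it through.** The protocol states no person-years, event count or rate, so there is no figure of its own to reproduce.

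**Inputs.** From the protocol: the formula (section 8.7.1); N = 216 patients in the last interim report and n = 34 anticipated with moderate disease (section 8.5); n = 11 with moderate disease at 5% adoption (Table 1). Assumed: one event (E = 1), strata of 10 and 20, mean exposure of 540 days or 1.5 years, and the event timings named below.

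**Step 1: what is exact and what is not.** With m the mean exposure,

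- plan: PY = (N·m − E·m/2)/365.25
- time to first event: PY = (N·m − R)/365.25, where R is the exposure of event patients after their event.

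N·m is total exposure, with no approximation. The plan replaces R by E·m/2 and is right only when the two agree.

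**Step 2: size with one event.** Each entry is the planned rate relative to the rate on true time to first event.

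| N | Exposure ended at the event (R = 0): N/(N − 0.5) | Event on day 0, treatment continued, average exposure (R = m): (N − 1)/(N − 0.5) |
|---|---|---|
| 216 | 216/215.5, 0.23% too high | 215/215.5, 0.23% too low |
| 34 | 34/33.5, 1.5% too high | 33/33.5, 1.5% too low |
| 11 | 11/10.5, 4.8% too high | 10/10.5, 4.8% too low |
| 10 | 10/9.5, 5.3% too high | 9/9.5, 5.3% too low |

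**Step 3: the same in days.** Event on day 1, other patients at 540 days each.

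- N = 20: true (19 × 540 + 1)/365.25 = 28.09 PY. If treatment continues, the plan gives (10,800 − 270)/365.25 = 28.83 PY, a rate 2.6% too low. If it stops, the total is 10,261 days and the mean 513.05, so the plan gives 27.39 PY, a rate 2.6% too high.
- N = 10: true 13.31 PY. The plan gives 14.05 PY (5.2% too low) or 12.64 PY (5.3% too high).

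**Step 4: event patient far from the mean.** Take a mean of 1.5 years, an event patient with 5 years of exposure and an event on day 7 (0.019 years), so R = 4.981 years.

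- N = 216: plan 323.25, true 319.02 PY, 1.3% too low.
- N = 34: plan 50.25, true 46.02 PY, 8.4% too low.
- N = 11: plan 15.75, true 11.52 PY, 26.9% too low.

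With one event the overstatement cannot exceed N/(N − 0.5). The understatement has no comparable cap, because R can exceed m.

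**Step 5: one event outside exposure** (mean 1.5 years).

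- N = 216, no true event: the rate goes from 0 to 1/323.25 = 3.1 per 1,000 PY.
- N = 216, one true event: from 1/323.25 = 0.31 to 2/322.5 = 0.62 per 100 PY.
- N = 34, one true event: from 1/50.25 = 1.99 to 2/49.5 = 4.04 per 100 PY.

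**The case against.** The case for leaving the text alone has four parts.

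- **The sponsor has only aggregates.** A disclosed mid-exposure assumption is a recognised approximation under that limit, and its error has no fixed direction. This explains the formula. It does not make it necessary, because summed time to first event is an aggregate too.
- **The denominator error is small beside sampling error.** With one event, an exact Poisson 95% interval runs from about 0.03 to 5.6 times the estimate (used here only as a yardstick). A shift of 0.2% to 5% is minor by comparison. This stands.
- **On-exposure events are evidently meant.** The note places the event within exposure and speaks of censoring, and baseline is the start of emicizumab (section 8.3.2). A reader might infer that the protocol intends to count events from before treatment; the text does not support that. What remains is that the restriction is implied and never written, and that the period after stopping is not addressed. An analysis plan not at hand might settle the window, but the estimator is fixed here.
- **Few cases need checking.** The registry's report gives detail on each patient with a primary event. A reader might infer that the error cannot be put right afterwards. That goes too far: the registry, and perhaps the sponsor from that detail, could probably check the cases.

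**Conclusion.** The point holds in a limited form. The half-mean deduction does not censor at the event, and its error can go either way. With one event in a patient of average exposure, it is about 0.2% at N = 216, up to about 1.5% at N = 34 and about 5% at N = 10 or 11. It is larger when a long-exposed patient has an early event. The overall result is hardly touched; sparse strata are where it can show. The unbounded numerator could matter more: one event outside exposure makes a zero rate non-zero or doubles a one-event rate. All timings and mean exposures are assumed, since the documents give none.

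Three further readings go beyond the documents.

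- That the person-years as a whole are imputed: N × mean is exact.
- That the registry certainly holds the event dates: start of exposure, exposure duration and follow-up are supported, but no section says that event or stop dates are recorded.
- That the error reaches 11% to 18%: this needs an event in 20% to 30% of a subgroup, for example (1 − 0.2)/(1 − 0.1) = 0.89 and (1 − 0.3)/(1 − 0.15) = 0.82. The formula is prescribed only for TE, TMA and anaphylaxis, where such a fraction would be realistic only in a stratum of a few patients. Other adverse events are reported as number and percentage (section 8.7.2).

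**What to change.** In section 8.7.1, for each of TE, TMA and anaphylaxis, have the registry supply per stratum:

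- (a) the number of patients with a first event after the first emicizumab dose and within a stated at-risk window;
- (b) the summed days from first dose to first event or to the end of that same window, whichever comes first.

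The rate is then (a) / ((b)/365.25). The same window must govern both parts. The documents give no basis for its length after stopping, so the sponsor should state and justify it. Keep the half-exposure imputation only for events whose date is unavailable, and report how many there are.

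The cost is two extra aggregate totals per table cell in the registry's annual report. No patient-level data would move, so sections 8.8 and 9.1 are respected. The change depends on event dates being recorded, which the protocol implies but does not state, and on the registry agreeing to produce the totals. Both should be confirmed first.
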